Patients from the pivotal phase who enter the OLE will taper their blinded IMP while simultaneously titrating their OLE IMP (GWP42003-P) over 4 days according to the titration regimen, an example titration regimen up to 40 mg/kg/day over 4 days is shown in Table 8.1.2-2. No further titration will be required for patients in the pilot phase; they will remain on the same GWP42003-P dose going into the OLE phase. Daily safety checks will be made during the first week of OLE IMP dosing. GWP42003-P may be discontinued at any time during the OLE phase, at the discretion of the investigator (see Section 9.1.2).

Table 8.1.2-2 Example Titration Regimen: Transition to the OLE Phase (Pivotal Phase Only)						
Day	Blinded IMP Dosage ¹	OLE IMP Dosage ¹	Total Daily IMP Dose (Patients Randomized to Placebo) ²	Total Daily IMP Dose (Patients Randomized to GWP42003-P) ²		
15	20 mg/kg (am/pm)	0	0	40 mg/kg		
16	15 mg/kg (am/pm)	5 mg/kg (am/pm)	10 mg/kg	40 mg/kg		
17	10 mg/kg (am/pm)	10 mg/kg (am/pm)	20 mg/kg	40 mg/kg		
18	5 mg/kg (am/pm)	15 mg/kg (am/pm)	30 mg/kg	40 mg/kg		
19 onwards	0	20 mg/kg (am/pm)	40 mg/kg	40 mg/kg		

Volumes of IMP to be taken each day will be calculated using the patient's weight and the required dose.

²Patients may taper to and remain on a lower dose if unable to tolerate the target dose.

²Patients may taper to and remain on a lower dose if unable to tolerate the target dose.

EudraCT Number: 2015-004904-50

Protocol V3 20Sep16

Following the end of treatment, all patients will commence a taper period (tapering 10% per day for 10 days). Patients who withdraw early should also begin the taper period following the withdrawal visit (unless continued dosing is not possible due to an AE). Patients who discontinue IMP during the OLE phase should also begin the taper period following the investigator's decision to discontinue. The IVRS/IWRS will generate the patient's daily IMP dosing volumes for the 10-day taper period.

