9.1.1.2 Visit 2 (Day 1 [+3 Days])

This visit will occur up to 7 (+3) days after Visit 1 (screening). Patients who satisfy all eligibility criteria (Section 6) during the screening period will be assigned GWP42003-P (pilot phase) or randomly allocated to GWP42003-P or matching placebo (pivotal phase) using the IVRS/IWRS (Section 9.2.2). Eligible patients must begin treatment within 7 days of their video-EEG screening assessment. The following will be collected/assessed prior to the patient receiving IMP:

- Concomitant medication review (Section 9.2.5).
- Physical examination (Section 9.2.6).
- Vital signs (Section 9.2.7).
- CGIC memory aid (Section 9.2.12.1).
- PGIC memory aid (Section 9.2.12.2).
- Vineland-II (Section 9.2.12.3).
- Caregiver diary review (Section 9.2.13) for:
 - Spasm/seizure information.
 - Changes in concomitant AEDs.
 - Usage of rescue medication.
 - AEs.
- AEs (Section 12).

Patients will receive sufficient IMP for 2 weeks of dosing. Patients in the pilot phase will remain in the clinic as inpatients during the 4-day titration period. For all patients, the first dose of IMP will be taken in the clinic on the morning of Day 1 with

EudraCT Number: 2015-004904-50

Protocol V3 20Sep16

an ECG assessment between 3 and 5 hours postdose (Section 9.2.8). For patients involved in the pivotal phase of the trial, a PK blood sample will be taken, provided the risk/benefit outcome is favorable in the investigator's opinion (Section 9.2.11). If a PK blood sample is collected, the investigator must note the sampling time and the dosing times of IMP and of any concomitant AEDs taken that day and the previous day. Patients will titrate to their target dose of GWP42003-P (or equivalent volume of placebo in the pivotal phase; Section 8.1.2) and will continue at this dose, or the highest tolerated dose up to 40 mg/kg/day, for the remainder of the 2-week treatment phase. During this time, the patient's current IS therapy may be continued or tapered, at the discretion of the investigator. All non-pharmacological interventions for epilepsy (including ketogenic diet and any neurostimulation devices for epilepsy) must remain stable during the pilot and pivotal phases of the trial. Following Visit 2, daily safety checks will be made during the first week of IMP dosing.

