9.1.1.4 Visit 3 (Day 4 [+1 Day])

This visit will occur 3 (+1) days after Visit 2. The following will be collected/assessed:

- Concomitant medication review (Section 9.2.5).
- Vital signs (Section 9.2.7).
- ECG (prior to the day's first dose of IMP; Section 9.2.8).
- Clinical laboratory samples (blood and urine [if possible]; Section 9.2.10) for:
 - Serum biochemistry.

- Hematology.
- Urinalysis.
- Caregiver diary review (Section 9.2.13) for:
 - Spasm/seizure information.
 - IMP usage.
 - Changes in concomitant AEDs.
 - Usage of rescue medication.
 - AEs.
- AEs (Section 12).

All patients will take their IMP in the clinic with an additional ECG assessment between 3 and 5 hours postdose (Section 9.2.8). Patients in the pilot phase will then be discharged from the clinic.

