9.1.1.5 Visit 4 (Day 15 [+3 Days]): End of Pilot or Pivotal Phase/Withdrawal

This visit will occur 14 (+3) days after Visit 2 or earlier if the patient withdraws from the pilot or pivotal phase of the trial. The following will be collected/assessed:

- Concomitant medication review (Section 9.2.5).
- Physical examination (Section 9.2.6).
- Vital signs (Section 9.2.7).
- ECG (prior to the day's first dose of IMP; Section 9.2.8).
- Video-EEG (Section 9.2.9).
- Clinical laboratory samples (blood and urine [if possible]; Section 9.2.10) for:
 - Serum biochemistry.
 - Hematology.
 - Urinalysis.
- **Pivotal phase only**: PK blood sampling (prior to the day's first dose of IMP, provided the risk/benefit outcome is favorable in the investigator's opinion; Section 9.2.11).
- CGIC (Section 9.2.12.1).

- PGIC (Section 9.2.12.2).
- Caregiver diary review (Section 9.2.13) for:
 - Spasm/seizure information.
 - IMP usage.
 - Changes in concomitant AEDs.
 - Usage of rescue medication.
 - AEs.
- AEs (Section 12).

Patients will take their IMP in the clinic with an additional ECG assessment between 3 and 5 hours postdose (Section 9.2.8). For patients involved in the pivotal phase of the trial, a further PK blood sample will be taken, provided the risk/benefit outcome is favorable in the investigator's opinion (Section 9.2.11). If PK blood samples are collected, the investigator must note the sampling times and the dosing times of the IMP and of any concomitant AEDs taken that day and the previous day. All IMP will be collected and compliance reviewed.

Patients who have successfully completed the pilot or pivotal phase will have the opportunity to receive GWP42003-P during the subsequent OLE phase at Visit 4. Patients from the pilot phase who enter the OLE phase will remain at the target dose which was reached during the pilot phase. Patients from the pivotal phase who enter the OLE phase will receive sufficient blinded IMP for tapering along with sufficient OLE IMP (GWP42003-P) for simultaneous titration and subsequent dosing for 2 weeks. All patients in the pivotal phase who enter the OLE phase will transition to the target dose of GWP42003-P (in a blinded manner; Section 8.1.2) and may continue at this dose, or the highest tolerated dose up to 40 mg/kg/day, for the remainder of the OLE phase. Following Visit 4, daily safety checks will be made during the first week of GWP42003-P dosing.

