9.1.2.2 Visit 5 (Day 19 [+1 Day])

This visit will occur 18 (+1) days after Visit 2. The following will be collected/assessed:

- Concomitant medication review (Section 9.2.5).
- Vital signs (Section 9.2.7).
- ECG (Section 9.2.8).
- Clinical laboratory samples (blood and urine [if possible]; Section 9.2.10) for:
 - Serum biochemistry.
 - Hematology.
 - Urinalysis.
- Caregiver diary review (Section 9.2.13) for:
 - Spasm/seizure information.
 - IMP usage.
 - Changes in concomitant AEDs.
 - Usage of rescue medication.
 - AEs.
- AEs (Section 12).

All patients will take their IMP in the clinic. For patients transitioning from the pivotal phase to the OLE a PK blood sample will be taken, provided the risk/benefit outcome is favorable in the investigator's opinion (Section 9.2.11). If a PK blood sample is collected, the investigator must note the sampling time and the dosing times of IMP and of any concomitant AEDs taken that day.

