9.2.7 Vital Signs

Vital signs measurements (systolic and diastolic blood pressure, pulse rate, body temperature and respiratory rate), taken in a supine position at rest for 5 minutes, will be completed alongside the physical examination. The methods/procedures employed for vital signs measurements must be consistent throughout the trial, where possible. Any deviation in methods used must be reported to the study monitor.

9.2.8 12-lead Electrocardiogram

ECG recordings will be performed after 5 minutes in a supine position. A physician must review the ECG immediately (annotated, signed and dated) and any abnormal findings considered to indicate significant medical history or AEs must be recorded appropriately on the CRF. Additional ECG measurements can be taken at any time during the trial, if clinically indicated.

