2.1.3 Addition of a Pilot Phase to Confirm Safety

Due to the lack of safety data in infants under 2 years of age, safety will be confirmed in a small group of patients in a hospital environment (pilot phase) before proceeding to the pivotal investigations. Therefore, the trial will be performed as 2 separate phases (pilot and pivotal) which will be run sequentially. All patients in the pilot phase will receive GWP42003-P (open-label) while all patients in the pivotal phase will be randomly allocated to GWP42003-P (1 of 2 dose levels) or matching placebo in a double-blind manner. As infants younger than 6 months are particularly vulnerable, all patients in the pilot phase will be over 6 months of age. The pivotal phase will only be enrolled after the DSMC

EudraCT Number: 2015-004904-50 Protocol Amendment 1 V1 31May16

has reviewed data from the pilot phase and has confirmed that there are no safety issues.

Due to the rapid titration of the investigational medicinal product (IMP), all patients in the pilot phase will remain in the clinic as inpatients during the 4-day titration period. In both phases, compulsory clinic-based assessments will take place at the end of the titration period (i.e., Day 4) and OLE transition period (i.e., Day 19). In addition, daily safety checks will be made during the first week of IMP dosing during the pilot and pivotal phases (i.e., Days 1–7) and during the first week of OLE IMP dosing (i.e., Days 16–22).

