⁴Safety follow-up visit is to occur 28 (+3) days after date of final dose (including tapered dose); weekly (±3 days) telephone calls must be made during the follow-up period. Each safety telephone call will conduct the same assessments as listed for safety follow-up visit.

⁵Based on assessment of clinical laboratory and video-EEG results.

 $^{^6\}mathrm{ECG}$ to be performed between 3 and 5 hours after the day's first dose of IMP only.

⁷ECG to be performed both prior to the day's first dose of IMP and between 3 and 5 hours after this dose.

⁸Only for patients involved in the pivotal phase, and progressing to the OLE from the pivotal phase. To be conducted only if the risk/benefit outcome is favorable, in the investigator's opinion.

⁹Memory aid only (worksheet completed).

¹⁰If necessary, IMP will also be dispensed for taper period.

¹¹IMP usage to be recorded on a dosing schedule which will form part of the paper diary

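### Up to 64 placebo infants who move to active drug in the extension have no ECG required 3-5 hours after an active dose; active-arm infants have three (minor, design only)

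*Protocol*

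**What the plan says.** Timed ECGs belong to the two-week phase. At Visit 2 (Protocol 9.1.1.2) the first dose is given in the clinic with "an ECG assessment between 3 and 5 hours postdose". At Visit 3 (9.1.1.4), "All patients will take their IMP in the clinic with an additional ECG assessment between 3 and 5 hours postdose", on top of a pre-dose ECG. Visit 4 (9.1.1.5) has the same pair. Footnotes 6 and 7 to the schedule in Appendix 1, copied in SAP Table 1, attach these timings to Visits 2, 3 and 4 and to no other visit.

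The switch to active drug comes after Visit 4. Section 8.1.2 states: "Patients from the pivotal phase who enter the OLE will taper their blinded IMP while simultaneously titrating their OLE IMP (GWP42003-P) over 4 days". In the example in Table 8.1.2-2, a placebo infant receives 0 mg/kg of active drug on Day 15, then 10, 20, 30 and 40 mg/kg/day on Days 16 to 19.

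Visit 5 (9.1.2.2, Day 19 with a one-day window) lists an ECG without a time, then says: "All patients will take their IMP in the clinic. For patients transitioning from the pivotal phase to the OLE a PK blood sample" follows, if the investigator judges it acceptable. Visits 6-12 also list untimed ECGs. Section 9.2.8 gives no time relative to dose, but allows more recordings: "Additional ECG measurements can be taken at any time during the trial, if clinically indicated".

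**The concern.** In the example regimens, a placebo infant entering the extension goes through the same four-day rise to 40 mg/kg/day as a high-dose infant did on Days 1-4. The protocol asked for ECGs at a fixed post-dose time during that earlier rise and asks for none during this one. A pre-dose ECG at Visit 5 complies with the text.

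Two features of the protocol give this some weight. ECG is part of the extension's primary safety endpoint (4.1.1.3). Section 10 also makes withdrawal mandatory for a confirmed QTcB of 500 msec or more, or a shift of 60 msec or more from baseline. That rule applies to an ECG at any time, so when the recordings are made affects what it can detect. At stake is a small gap in safety monitoring for infants newly exposed to the drug, not any efficacy comparison.

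**Working it through.** **Group size.** Section 13.1 gives 192 infants randomised 1:1:1. 192 / 3 = 64 on placebo, which matches the stated figure. Extension entry is optional (9.1.1.5) and open only to those who complete, so 64 is a ceiling. The documents give no entry rate.

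**Required 3-5 hour ECGs on active drug, by origin.**
- Active arms: Visits 2, 3 and 4 = 3.
- Placebo arm: Visits 2, 3 and 4 are on placebo and Visits 5-12 are untimed = 0.
- Untimed ECGs scheduled for extension participants: Visits 5 to 12 = 8, plus one at the end of taper.

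**What an ECG at Visit 5 follows, on schedule, 40 mg/kg/day example (Table 8.1.2-2).**
- Pre-dose on Day 19: the last two active doses are both 15 mg/kg (Day 18), total 30 mg/kg. The first target-level dose has not yet been given.
- At 3-5 hours post-dose on Day 19: the last two are 15 and 20 mg/kg, total 35 mg/kg. This follows the first target-level dose, not a full 40 mg/kg day.
- Comparator: by Table 8.1.2-1, the on-schedule post-dose ECG at Visit 3 in the high-dose arm also follows only the first 20 mg/kg dose, and the one at Visit 2 follows the first 5 mg/kg dose.

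**Next scheduled ECG.** Visit 6 is Day 29 ± 3, so Day 26 to 32. Counted from Day 19: 26 - 19 = 7 days to 32 - 19 = 13 days.

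**Does Visit 5 fall on a target-dose day?** Visit 4 is defined by "This visit will occur 14 (+3) days after Visit 2", so it can fall on Day 15 to 18; Visit 5 falls on Day 19 or 20. Assumptions: titration starts the day after Visit 4, in steps of 10 mg/kg/day. Then

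dose on the day of Visit 5 = min(target, 10 × (Visit 5 day − Visit 4 day)).

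| Target (mg/kg/day) | Visit 5 on | Visit 4 Day 15 | Day 16 | Day 17 | Day 18 |
|---|---|---|---|---|---|
| 40 | Day 19 | 40 | 30 | 20 | 10 |
| 40 | Day 20 | 40 | 40 | 30 | 20 |
| 20 | Day 19 | 20 | 20 | 20 | 10 |
| 20 | Day 20 | 20 | 20 | 20 | 20 |

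Target is reached in 3 of 8 combinations at 40 mg/kg/day and in 7 of 8 at 20 mg/kg/day. These are unweighted counts, not probabilities. Two targets are shown because the High Dose Level is left to the DSMC. In all 8 combinations the infant is on active drug (at least 10 mg/kg/day), so a timed Visit 5 ECG raises the count from 0 to 1 even when it precedes the target dose.

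**Low Dose arm.** This arm receives 50% of the High Dose Level in the pivotal phase. Sections 4.1 and 9.1.1.5 refer to the extension target without saying whether these infants move up. If they do, a further group of up to 64 has three timed ECGs on active drug but none at its extension dose.

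**Clinic time.** The suggested PK window on Day 19 is 4-12 hours after the first dose (9.2.11). Its overlap with 3-5 hours is 4-5 hours, so one stay can cover both.

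**The case against.** The strongest reply is that this is a preference. The protocol nowhere promises timed ECGs in the extension, whose aim is long-term safety. Intensive ECG timing in the controlled phase followed by routine recordings is a coherent plan. That stands in part: the documents give no time to peak concentration and no QT signal, so no risk is demonstrated. What remains is that these infants begin active drug in the extension, so the phase with timed ECGs never covers their exposure.

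There are other safeguards: daily safety checks on Days 16-22, ECGs when clinically indicated, DSMC review of pilot and blinded pivotal safety data, and an end-of-taper ECG. They lessen the consequence, but none requires a 3-5 hour ECG on active drug.

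Stronger readings that a reader might infer are not supported:
- That these infants have no ECG on active drug. Eight are scheduled at Visits 5-12; only the timing is missing.
- That Amendment 1 commits to matching ECGs. Its Section 2.1.3 says "compulsory clinic-based assessments will take place at the end of the titration period (i.e., Day 4) and OLE transition period (i.e., Day 19"), which pairs the two visits but does not mention ECG timing.
- That moving the ECG changes what is observed from 30 to 40 mg/kg/day. By 3-5 hours, only the first 20 mg/kg dose of that day has been given.
- That reported results are affected. SAP Section 5 says only pilot patients were included, and they have timed ECGs on active drug at Visits 2-4.

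**Conclusion.** The point holds as a minor design gap. As designed, up to 64 of 192 infants would have 0 required 3-5 hour post-dose ECGs on active drug, against 3 in the active arms. That count is exact on the text. The number of infants is a ceiling, and the number actually affected is 0.

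The dose-day figures rest on the example regimen, 10 mg/kg/day steps and titration starting the day after Visit 4. The extension to the Low Dose arm depends on a target that the protocol leaves unsettled. The case is one of consistency with the protocol's own early-dosing standard, and is worth acting on only because the correction is cheap.

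**What to change.** In Section 9.1.2.2, the Visit 5 text of the synopsis and Appendix 1, require the single existing Visit 5 ECG at 3-5 hours after the in-clinic dose for every infant transitioning from the pivotal phase. Applying it to all of them keeps the blind. The model is footnote 6, which sets one post-dose ECG at Visit 2. Record the time since dose and the dose level that day. Align the schedule copied in SAP Table 1; no analysis changes.

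Cost: a footnote, matching text in those places and two CRF fields, handled within a protocol amendment. No procedure is added. Families not giving the PK sample wait 3-5 hours after the dose, and Visit 5 has no pre-dose ECG. A second ECG, as at Visits 3 and 4, is not asked for.

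Limits to state: on schedule, the first active dose is still not captured; Visits 6-12 stay untimed; and if Visit 4 is late, Visit 5 may come before the target dose.

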9.1.2.3 Visit 6 (Day 29 [±3 Days])

This visit will occur 28 (±3) days after Visit 2. Collection of Visit 6 assessments earlier than Day 29 (i.e., on Day 26, 27, or 28) must only occur if there have been no witnessed spasms over the preceding 48 hours (minimum). The following will be collected/assessed:

- Concomitant medication review (Section 9.2.5).
- Physical examination (Section 9.2.6).
- Vital signs (Section 9.2.7).
- ECG (Section 9.2.8).
- Video-EEG (Section 9.2.9).
- Clinical laboratory samples (blood and urine [if possible]; Section 9.2.10) for:
 - Serum biochemistry.
 - Hematology.
 - Urinalysis.
- CGIC (Section 9.2.12.1).
- PGIC (Section 9.2.12.2).
- Caregiver diary review (Section 9.2.13) for:
 - Spasm/seizure information.
 - IMP usage.
 - Changes in concomitant AEDs.
 - Usage of rescue medication.
 - AEs.
- AEs (Section 12).

All IMP will be collected and compliance reviewed. Patients will then receive sufficient IMP for 2 weeks' dosing.

EudraCT Number: 2015-004904-50

Protocol V3 20Sep16

9.1.2.4 Visit 7 (Day 43 [±3 Days])

This visit will occur 42 (± 3) days after Visit 2. The following will be collected/assessed:

- Concomitant medication review (Section 9.2.5).
- Physical examination (Section 9.2.6).
- Vital signs (Section 9.2.7).
- ECG (Section 9.2.8).
- Video-EEG (Section 9.2.9).
- Clinical laboratory samples (blood and urine [if possible]; Section 9.2.10) for:
 - Serum biochemistry.
 - Hematology.
 - Urinalysis.
- CGIC (Section 9.2.12.1).
- PGIC (Section 9.2.12.2).
- Caregiver diary review (Section 9.2.13) for:
 - Spasm/seizure information.
 - IMP usage.
 - Changes in concomitant AEDs.
 - Usage of rescue medication.
 - AEs.
- AEs (Section 12).

All IMP will be collected and compliance reviewed. Patients will then receive sufficient IMP for 4 weeks' dosing.

9.1.2.5 Visit 8 (Day 71 [±3 Days])

This visit will occur 70 (\pm 3) days after Visit 2. The following will be collected/assessed:

- Concomitant medication review (Section 9.2.5).
- Physical examination (Section 9.2.6).

- Vital signs (Section 9.2.7).
- ECG (Section 9.2.8).
- Clinical laboratory samples (blood and urine [if possible]; Section 9.2.10) for:
 - Serum biochemistry.
 - Hematology.
 - Urinalysis.
- CGIC (Section 9.2.12.1).
- PGIC (Section 9.2.12.2).
- Caregiver diary review (Section 9.2.13) for:
 - Spasm/seizure information.
 - IMP usage.
 - Changes in concomitant AEDs.
 - Usage of rescue medication.
 - AEs.
- AEs (Section 12).

All IMP will be collected and compliance reviewed. Patients will then receive sufficient IMP for 8 weeks of dosing.

9.1.2.6 Visit 9 (Day 127 [±7 Days])

This visit will occur 126 (\pm 7) days after Visit 2. The following will be collected/assessed:

- Concomitant medication review (Section 9.2.5).
- Physical examination (Section 9.2.6).
- Vital signs (Section 9.2.7).
- ECG (Section 9.2.8).
- Video-EEG (Section 9.2.9).
- Clinical laboratory samples (blood and urine [if possible]; Section 9.2.10) for:
 - Serum biochemistry.
 - Hematology.

- Urinalysis.
- CGIC (Section 9.2.12.1).
- PGIC (Section 9.2.12.2).
- Caregiver diary review (Section 9.2.13) for:
 - Spasm/seizure information.
 - IMP usage.
 - Changes in concomitant AEDs.
 - Usage of rescue medication.
 - AEs.
- AEs (Section 12).

All IMP will be collected and compliance reviewed. Patients will then receive sufficient IMP for 12 weeks of dosing.

9.1.2.7 Visit 10 (Day 211 [±7 Days])

This visit will occur 210 (\pm 7) days after Visit 2. The following will be collected/assessed:

- Concomitant medication review (Section 9.2.5).
- Physical examination (Section 9.2.6).
- Vital signs (Section 9.2.7).
- ECG (Section 9.2.8).
- Video-EEG (Section 9.2.9).
- Clinical laboratory samples (blood and urine [if possible]; Section 9.2.10) for:
 - Serum biochemistry.
 - Hematology.
 - Urinalysis.
- CGIC (Section 9.2.12.1).
- PGIC (Section 9.2.12.2).
- Vineland-II (Section 9.2.12.3).
- Caregiver diary review (Section 9.2.13) for:

- Spasm/seizure information.
- IMP usage.
- Changes in concomitant AEDs.
- Usage of rescue medication.
- AEs.
- AEs (Section 12).

All IMP will be collected and compliance reviewed. Patients will then receive sufficient IMP for 12 weeks of dosing.

